9.4 Determination of sample size

The primary endpoint of the NeoRad trial is DFS. To determine the sample size, we assumed that DFS is an exponential parameter and amounts to a 5-year rate of approximately 80% for high-risk breast cancer. This value matches the risk detected in the Gepar trials. NeoRad will also include patients with a slightly lower risk (nodal-negative luminal B tumors and triple negative, Her2 positive cases receiving new postneoadjuvant therapy). Therefore, we expect less events and calculate a higher sample size. We further expect to include less high-risk patients because of competing trials that include only high-risk breast cancer patients. That is why we calculate a marginally increased number to treat.

Therefore, we hypothesise that the 10-year DFS rate will show an improvement from 70% in the control arm to 76.5% in the experimental arm (HR=0.75), which would be considered clinically relevant. In order to detect a difference of this magnitude with a power of 80%, 379 events and a sample size of 1826 patients, 913 in each arm using a 1:1 randomisation, are required to reject the null hypothesis of no improvement on a two-sided type I error level of 0.05. A cumulative drop-out rate of 10% in 10 years is included in these calculations. This calculation is based on an assumed exponential shape of the survival curves and the drop-out process, 4 years of recruitment as well as a minimum follow-up period of six years for all patients and was performed with nQuery Advisor 7.0.

Test of exponential survival (n large) and exponential dropout (*statistics by German breast Group*):

Test significance level,	0.050
1 or 2 sided test?	2
Length of accrual period	4.00
Maximum length of followup	10.00
Common exponential dropout rate, d	0.0105

Group 1 exponential parameter,	0.0268
β_1	
Group 2 exponential parameter,	0.0357
β_2	
Hazard ratio, $h=\beta_1 / \beta_2$	0.750
Power (%)	80
n per group	913
Total number of events required, E	379

Conversion to alternate rates for exponential survival curves

	DFS rates	D/o rate
Time t	10.0	10.0
Group 1 proportion β_1 at time t	0.765	0.900
median survival	25.911	65.788
exponential	0.0268	0.0105
parameter, β_1		
Group 2 proportion β_2 at time t	0.700	
median survival	19.434	
exponential	0.0357	
parameter, β_2		

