Randomization procedure	
Investigators will inform eligible patients about the NeoRad trial during the regular clinical consultation visits in the respective study site before or during NACT. The study permits inclusion of participants from the point of diagnosis until prior to the initial assessment of systemic therapy response. Informed consent will be obtained by the local radiation oncology department. A complementary translational study is planned to collect biomaterials. Patients can be enrolled in the translational study from the time of diagnosis until the first evaluation. In instances, where obtaining informed consent at the time of diagnosis is not feasible, the gynecologist may provide information regarding the trial and obtain informed consent for the translational study. Randomization is feasible from the point of enrollment in the study until prior to the initial evaluation of therapy response. All study related investigations and documentation of patients will be performed only after written informed consent was collected using the actual ethics committee approved patient information and consent form.
 
Patients fulfilling the inclusion-/exclusion criteria will be registered online in the eCRF. For each patient, a unique patient number for pseudonymized identification throughout the study will be generated.
 
Patients will be randomized at time of inclusion and before initial assessment of response to NACT 1:1 into one of the study arms, stratified by:

	
1) biological subtype: Strata: HER2-type (HER2/neu positive), HR+/HER2- type (no HER2/neu overexpression), triple negative
 
2) cN-Status (before start of NACT): Strata: cN+, cN-
 
3) type of planned surgery: Strata: BCS vs Mastectomy (NSM, SSM or radical)
 
The randomization plan will be generated by a validated SAS program and undergoes strict access control. Treatment groups will be allocated by the IWRS system integrated in the eCRF.

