3.2 Secondary objectives

Assessment and comparison between randomized arms of

- 1) time to local recurrence [in affected breast] (LR) as a first site of recurrence: recurrence in affected breast counts as an event; regional recurrence, distant recurrence, contralateral breast cancer, invasive non-breast cancer, death due to any cause are considered competing risks.
- 2) time to regional recurrence (RR) as a first site of recurrence: recurrence in the regional lymph nodes counts as an event, local recurrence, distant recurrence, contralateral breast cancer, invasive non-breast cancer, death due to any cause are considered competing risks.
- 3) distant disease-free survival (DDFS): distant recurrence, invasive non-breast cancer and death due to any cause are considered as events.
- overall survival (OS): death due to any cause is considered as an event.
- 5) breast cancer specific survival (BCSS): death due to breast cancer is considered as an event; in case of unknown death cause all effort will be made to determine the cause; if at the time of analysis there are still any deaths due to the unknown reason, they will be counted as tumor-related (worst case principle).

Time for all time-to-event endpoints will be computed starting from randomization after end of NACT.

- 6) pathological complete remission (pCR, defined as ypT0/is ypN0) rates.
- 7) cosmetic results (5 Point Scoring System, key secondary objective and subjective
- 8) breast retraction assessment=BRA)
- 9) quality of life (EORTC C30 and EORTC QLQ-BR23)
- 10) rate of arm lymph edema >°I of the irradiated side
- 11) plexopathy >°I of brachial plexus of the irradiated side

12) acute (up to 3 months after the end of radiotherapy) and late (after 3 months) toxicity (CTC 5.0, LENT-SOMA)

Definitions of outcome measures (clinical Trials.gov):

1. local recurrence rate [in affected breast] (LR) [Time Frame: 6 to 10 years]
Rate of cancer that has recurred at the same location as the primary cancer. This is a way to measure how well the new treatment is working.
2. locoregional recurrence rate (LRR) [Time Frame: 6 to 10 years]
Rate of new cancer at any locations (regional lymph nodes, chest wall/mastectomy site) on side which was previously affected by the primary cancer.
This is a way to measure how well the new treatment is working.
3. disease metastases free survival (DMFS) [Time Frame: 6 to 10 years]

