4.5 Experimental arm

Patients randomized into the experimental arm will receive the planned neoadjuvant systemic treatment as in the standard arm of the trial. Two weeks after completion of neoadjuvant

systemic therapy, a re-assessment of the axillary lymph nodes is highly recommended with core needle biopsy in case of suspected residual lymph node metastasis to assess the response to NACT and also for the indication for post-neoadjuvant chemotherapy. In addition, a core needle biopsy or the primary tumor/ tumor region is highly recommended in any situation irrespective of clinical response. The decision to perform these biopsies is the responsibility of the treating study physician.

Radiotherapy will start as soon as the patient recovers and can receive radiotherapy. The dose regime is similar to that prescribed for standard of care arm. If possible, preoperative radiotherapy should start approximately 3 weeks (2-4 weeks) after finalizing NACT.

Approximately 3 weeks (2.5 - 6 weeks) after completion of radiotherapy, surgery will be performed according to the S3/AGO-guidelines. The patient presents 2 weeks after the completion of radiation therapy for the evaluation of acute side effects. The radiation oncologist will authorize the patient for surgery. The management of the axilla is illustrated in figure 2.

The overarching consensus from the existing body of evidence supports the notion that a delay in surgical intervention due to preoperative radiotherapy does not have negative adverse effects on patient outcomes. Therefore, this trial proceeds under the assumption that a delay in surgery occasioned by preoperative radiotherapy is not a concern, and is in fact, a strategic part of the treatment protocol that could enhance patient outcomes. Neoadjuvant radiotherapy, aiming to sterilize tumor cells to curb their proliferation and metastatic potential.

In cases where patients have suspect lymph nodes (LK) that cannot be biopsied, the treatment approach should be based on the clinical stage as assessed by the examiner. This means that the treatment protocol for these patients should proceed as if they are either N+ or N-, depending on the examiner's evaluation.

[figure not shown]

Figure 2: Axilla management within NeoRad Trial

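### The sample size applies HR 0.75 from randomisation and makes no allowance for the NACT period, when both arms are treated alike; the stated 80% power therefore depends on assumptions that the protocol does not give

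*Protocol*

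**What the plan says.** Section 9.4 states the requirement as follows: "In order to detect a difference of this magnitude with a power of 80%, 379 events and a sample size of 1826 patients", which "are required to reject the null hypothesis of no improvement on a two-sided type I error level of 0.05". The inputs are exponential hazards of 0.0268 and 0.0357 per year (HR 0.750), four years of accrual and ten years of maximum follow-up. For losses, "A cumulative drop-out rate of 10% in 10 years is included in these calculations". On shape, "This calculation is based on an assumed exponential shape of the survival curves and the drop-out process, 4 years of recruitment". There is no lag term.

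The synopsis (randomization procedure) says: "Patients will be randomized at time of inclusion and before initial assessment of response to NACT 1:1 into one of the study arms". The organisation chapter and section 6.5 agree, and section 5.2 excludes patients already assessed for chemotherapy response. Section 4.5 says: "Patients randomized into the experimental arm will receive the planned neoadjuvant systemic treatment as in the standard arm of the trial". Preoperative radiotherapy then starts about three weeks after NACT.

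The synopsis, Table 1 in section 3.1 and section 9.3.1 count DFS from randomisation, but the footnote in section 3.1 counts from diagnosis. Section 3.2 says: "Time for all time-to-event endpoints will be computed starting from randomization after end of NACT".

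Section 9.2.1 analyses all randomised patients. Section 6.7 excludes, and allows replacement of, those who develop distant metastasis or withdraw before local treatment. Section 4.2 plans the end of follow-up for Q1 2034, ten years after recruitment starts.

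**The concern.** A constant HR of 0.75 from time zero means that the experimental arm already benefits during chemotherapy, when its treatment is the same as the control arm's. The model would fit a trial that randomises once NACT is finished. Section 3.2 still describes that trial, but the randomisation sections do not.

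There are two ways to lose power. If DFS events occur during NACT, they carry no treatment effect and dilute the log-rank comparison. If almost none occur, each patient spends part of a fixed calendar follow-up not at risk, and fewer events accrue. The margin is thin: the design expects 386 events and needs 379, about 2%. There is no efficacy interim analysis, so a shortfall would be noticed late.

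**Working it through.** **Inputs from section 9.4:** two-sided alpha 0.05; control hazard −ln(0.70)/10 = 0.0357; HR 0.75; drop-out −ln(0.90)/10 = 0.0105 per year; 913 per arm; uniform accrual over 4 years; analysis at 10 years.

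**Step 1, the plan's own figure.** Schoenfeld: D = 4 × (1.960 + 0.842)² / (ln 0.75)² = 31.40 / 0.0828 = 379. With the stated accrual, drop-out and follow-up, 913 per arm gives 386 expected events. Numerical log-rank power is 80.3%. The stated calculation reproduces.

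**Step 2, adding the identical-treatment period.** The protocol gives no NACT duration, so 3 to 7 months from randomisation to the end of NACT is an assumption. Hazards are equal in both arms during this period and have HR 0.75 after it. Three cases:

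- A: control hazard 0.0357 in both arms during NACT, planned hazards after it.
- B: no events during NACT, planned hazards after it.
- C: no events during NACT, with the later control hazard raised so that 10-year control DFS is still 70%. For 6 months this is −ln(0.70)/9.5 = 0.0375.

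Power and expected events by Q1 2034, by numerical integration:

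| Period | A | B | C |
|---|---|---|---|
| 3 months | 77.0%, 387 (16 during NACT) | 79.1%, 374 | 80.0%, 383 |
| 4 months | 75.9%, 388 (22) | 78.7%, 371 | 79.9%, 382 |
| 6 months | 73.5%, 389 (32) | 77.9%, 363 | 79.7%, 380 |
| 7 months | 72.4%, 389 (37) | 77.5%, 359 | 79.6%, 379 |

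Hand check of A at 6 months: power ≈ Φ(√D/2 × share of events after NACT × |ln 0.75| − 1.96) = Φ(9.86 × 357/389 × 0.2877 − 1.96) = Φ(0.64) = 74%. Simulation of 3,000 trials per case gives 80.4% with no lag. At 6 months it gives 73.7% (A), 77.7% with 363 events (B) and 79.8% with 380 events (C).

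**Step 3, what the cases imply.** A turns HR 0.75 into an event-weighted average of 0.759 at 3 months and 0.771 at 7. B raises control 10-year DFS above the stated 70%: at 6 months, exp(−0.0357 × 9.5) = 71.3%. In B, 379 events arrive about two to six months after Q1 2034.

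**Step 4, reading 0.75 as an average from randomisation.** At the planned hazard, ln(HR after NACT) = ln(0.75) / share of events after NACT. With a share of 0.958 at 3 months this gives 0.74; with 0.903 at 7 months it gives 0.73. Keeping only the 76.5% ten-year rate needs a post-NACT HR of (0.2679 − 0.0178)/0.3388 = 0.738 at 6 months, and power is then 77.8%.

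**The case against.** The arithmetic in section 9.4 is correct for the model it states. DFS runs from randomisation, so 0.75 can be read as the average effect over the whole period. On that reading the 80% stands, and what is missing is a statement of that assumption.

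Case A is probably pessimistic. The listed DFS events are recurrences, contralateral or second cancers, and deaths. Locoregional progression during NACT (section 6.3) is not among them, and the exclusion in section 6.7 would remove distant metastases before local treatment. Case C keeps the protocol's stated 70% and 76.5% and loses almost nothing. Randomisation may also take place as late as the first response assessment, which shortens the period.

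These points stand, and they limit the size of the finding. They do not remove it. Section 9.2.1 contradicts section 6.7, so the document does not settle which events count. Case C needs a higher post-NACT control hazard than the 0.0357 in section 9.4. None of the three cases gains power.

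A reader might infer that the design delivers about 73% to 78% power. The documents do not support that as a fact: it rests on an assumed period and event rate, and it leaves out the near-80% case. A reader might also infer that the final analysis is fixed by date alone. The protocol gives a planned date and a required event count without saying which governs. That detail may be left to the SAP, so its absence is not an error in itself.

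**Conclusion.** The point holds as an unstated assumption in the power calculation, together with a contradiction about time zero. It is not an arithmetic error. The model in section 9.4 fits only the randomisation after NACT described in section 3.2, which the synopsis, the organisation chapter and section 6.5 contradict.

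For an assumed 3 to 7 months of identical treatment, power ranges from about 72% to just under 80%. The low end needs the planned hazard during NACT; there the event count is sufficient (387 to 389) but the effect is diluted. The middle, about 77% to 79%, comes with a shortfall to 374 to 359 events. The top needs an event-free NACT, 70% control DFS at ten years and a post-NACT HR of 0.75, all together. Dilution at the planned hazard and the event shortfall are alternatives and should not be added together.

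**What to change.** 1. Use one time zero for DFS in sections 3.1 (footnote and Table 1), 3.2 and 9.3.1, and reconcile the exclusion in section 6.7 with the ITT set in section 9.2.1.
2. In sections 9.4 and 4.1 and the synopsis, state the assumed time from randomisation to the end of NACT and the DFS event rate in it, and restate the power. Alternatively, declare 0.75 the average HR from randomisation and give the post-NACT HR it implies (about 0.74 for 3 months and 0.73 for 7 months at the planned hazard).
3. State that the final DFS analysis takes place at 379 events and not before Q1 2034. This guards against a low event count; it does not repair dilution, which only the restated power makes visible.

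The cost is a few sentences, a slightly lower stated power and possibly some months of extra follow-up. No patients are added.

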9.5 Interim analysis

The pre-planned early safety assessment after n=100 patients is described in detail in section 4.6. No interim analyses of efficacy with early stopping option are planned due to the fact that statistically significant differences in DFS and OS will first be measurable at a minimum of 5 years follow-up when the recruitment is completed and an interim analysis would not allow for a reduction of patient numbers to be randomized.

9.6 Additional procedures

Further details of the statistical analysis will be outlined in a Statistical Analysis Plan (SAP), which will be finalised prior to performing any efficacy analyses within the framework of the study. Questionable cases, notably with regard to allocation to the analysis sets, as well as severe protocol violations and event categories, will likewise be decided in a blinded way at the pre-analysis meeting.

10. ETHICAL AND REGULATORY REQUIREMENTS

10.1 Ethical conduct of the study

The study will be performed in accordance with (the) ethical principles that have their origin in the Declaration of Helsinki and are consistent with ICH/Good Clinical Practice/applicable regulatory requirements for patient data protection.

10.2 Ethics and regulatory review

The study will be performed according to current legal standards. The ICH E6 harmonised Tripartite Guideline for Good Clinical Practise, dating to 1997 and including Revision 2 from June 2017, will be taken into account. In Germany, the requirements according to the following documents will be fulfilled: Good clinical practice (GCP), all in their current versions. The coordinating investigator has at least fifteen years of experience in clinical trials for medical products.

As the radiation therapy is performed according to current established standards (approved by the DEGRO-Expertengremium, 20/11/2019), involvement of the Bundesamt für Strahlenschutz' (BfS) or reference to the 'Atomgesetz' are not required.

10.3. Informed consent

Each patient will be informed that participation in the study is completely voluntary, and that they may withdraw their participation in the trial at any time without having to declare any reasons. This will not lead to any disadvantage for the respective patient. If during the study procedure an adverse side effect occurs, the patient must inform the treating physician about this. The treating physician will inform the patient about the combined modality treatment used and its possible adverse events. At the same time, they will be informed about the nature and objectives of the study, expected advantages of the participation, possible risks of the study, and alternatives to the treatment.

The patient shall also receive the necessary information on the trial-specific insurance and their obligations with this respect. The patient will have sufficient time to decide and will be provided an opportunity to ask additional questions. Moreover, the patient will receive a written "patient information" (see Appendix 2) containing all relevant information for the patient's decision and the course of the study. The consent of the patient to participate must be obtained in writing before recruitment to the study. The informed consent form must be dated and signed by the patient.

Thereby, they declare their voluntary consent to participate in the study and the willingness to comply with the requirements of the trial and the instructions of the treating investigator (medical doctor) for the duration of the study. The investigator has to sign the informed consent form after the patient. There are two copies of the informed consent form: one for the patient and one to be kept by the investigator in his study documents. The informed consent is only valid after receiving the patient's and the investigator's signature. Thereafter, the patients can be entered into the study if they fulfil the selection criteria. With the declaration of consent, the patient agrees that the data on his disease are recorded within the framework of the clinical trial, and that they are transferred to the coordinating center in a pseudonymized way. Furthermore, the patient agrees that delegates from the responsible authorities or the coordinating center may have direct access to their original medical records for trial-related monitoring, audit, review, and regulatory inspection.

Each patient is assigned a number code by the central data collection point (GBG). There is no personal data collected allowing conclusions to be drawn about a person. The confidentiality obligation applies to the practitioners and the central data collection organisation. Patient data are collected at the treating centres and passed on to the central data collection group (GBG). Here, the names of the patients are pseudonymized. The study centre has pseudonymized data at the time of the analysis. The randomisation table is held by the GBG.

10.4 Changes to the protocol and informed consent form

Any modifications of the protocol, which may impact the conduct or potential benefits of the study, including changes of study objectives, procedures, or its design, as well as patient population, sample sizes, or significant administrative aspects (cf. § 10, Abs. 1 GCP-V for the decision criteria) will require a formal amendment to the protocol. Such amendment needs to be agreed upon by the coordinating center and the study chairmen. It requires a new application to the responsible ethics committee prior to implementation, according to § 10, Abs. 2 to 4 GCP-V. Administrative or technical changes to the protocol, such as minor corrections and/or clarifications that have no effect on conduction of the study nor the risk-benefit-ratio, will be agreed upon by the coordinating center and the study chairmen, and will be documented in a memorandum to the protocol. The competent ethics committee may be notified of such changes at the discretion of the coordinating investigator. The coordinating investigator need to assure that all amendments have been added to the study documents at any site involved in the trial.

10.5 Audits

In case of an audit by the coordinating center or an appropriate authority, the investigator will make all relevant documents available. If an audit visit by a regional authority is announced, the respective study site should inform the coordinating center and the study chairmen as well as the monitoring center (GBG Forschungs GmbH) as early as possible in order to allow for an appropriate preparation and support. The sponsor and the coordinating inspected

investigator or organisational institution of the study shall be informed about the result of the audit.

Internal quality reviews will take place at the meetings of the study participants. Therefore, the coordinating investigator reference board will instruct the participating study sites to present their primary documentations of the study procedures. The results will be discussed at the meetings to improve the quality of the procedures and documentation.

